6b Choice of Comparator: Control participants will receive placebo capsules containing 288 mg of rice protein (California Natural Products, Lathrop, CA), 109.3 mg microcrystalline cellulose (Stauber USA, Fullerton, CA), 4.3 mg Aerosil® 200 fumed silica (Vivion Inc., San Carlos, CA), and 4.3 mg magnesium stearate (Nitika Pharmaceutical Specialties, Maharashtra, India), and formulated into a capsule by Metagenics, Inc. (Gig Harbor, WA).

7 Objectives

A methodological limitation of assessing the efficacy of CD treatments is that the gut microbiome of CD subjects is highly personalized in terms of state and dynamics. By correlating time-resolved fluctuations in the gut microbiome of CD subjects with their concomitant changes in the profile of XN metabolites, BA profiles, and other markers of gut microbiome-associated biochemical activity as well as with established surrogate end-points of the disease, we hypothesize:

1) XN at the given dose will be safe and tolerable in adults with active CD;

2) XN will improve biomarkers and improve the Crohn's Disease Activity Index (CDAI) an activity index of CD activity;

3) We can identify a biological signature(s) of XN through its metabolic byproducts in blood, urine, and stool as well as its effect on bile acid reabsorption; and

4) Specific biological signature(s) of XN exposure will uniquely contribute to changes in CD-associated disease activity indices.

To test these hypotheses and generate a conceptual model, we define four Specific Aims:

Protocol

- Aim 1. Determine the clinical safety and tolerability of xanthohumol in adults diagnosed with CD. We will determine the safety and tolerability of xanthohumol in adults diagnosed with CD over 8 weeks in a Phase 2 trial. The primary hypothesis is that in the XN arm, the number of participants with an adverse event or abnormal lab value will not be more than 50% higher than the number in the placebo group.
- Aim 2. Assess changes in levels of inflammation and symptom severity related to CD.

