Data on adherence to the treatment protocol will be assessed qualitatively and quantitatively by asking participants if they have missed any doses, and why doses were missed if relevant, during each bi-weekly visit, plus by pill count at the week 4 and week 8 clinical visits by the Study Coordinator. A limited supply of product, adequate for 5 weeks, will be dispensed at the Randomization visit and at the Week 4 clinical visit.

11d Permitted concomitant care or intervention during trial

- Anti-inflammatory medications including oral 5-aminosalicylates (e.g., sulfasalazine, mesalamine)
- Immunomodulators (e.g. azathioprine, 6-mercaptopurine, methotrexate)
- Use of over-the-counter medications as indicated on the label for less than 2 days per week
- Multi-vitamin and/mineral
- Dietary supplements except as detailed below

Allowed emergency intervention during trial

• Glucocorticoids (e.g., prednisone, budesonide)

Prohibited concomitant care during trial

- Dietary supplements containing xanthohumol
- Dietary supplements containing flavonoids
- Other known "anti-inflammatories" including curcumin, turmeric, fenugreek, hops, rosemary, ginger, white willow, devil's claw, fish oil (doses>1 g/day), or quercetin.
- Anti-coagulant or anti-platelet prescription medications
- Antibiotic, antiparasitic, or antifungal medications orally or intravenously

12 Outcomes

Table	1
I HOIC	

OUTCOME	MEASURE	DESCRIPTION
Primary: Safety & Tolerab	ility	
Clinical Safety/Cumulative Toxicology	Liver (AST, ALT, GGT) and renal function (eGFR, BUN:Cr) tests plus hematology (CBC)	Routine clinical toxicology measures
Secondary: Clinical Status		
Gut inflammation	Fecal calprotectin	Enzyme-linked immunosorbent assay

Inflammation	Plasma pro-inflammatory	Flow cytometry-based multiplex assay
	cytokines (TNF-α, IL-1β,	C reactive protein from Quest Labs
	IL-2, IL-6, IL-8, IL-10,	C-reactive protein from Quest Labs
	and IL-12p70) and C-	
	reactive protein	
Composite Symptoms	Crohn's Disease Activity	Symptom severity will be determined
	Index (CDAI)	using the CDAI
Tertiary: Mechanistic Patl		
Metabolic byproducts of	XN and XN metabolites	Ultra-high-performance liquid
XN	in blood, urine and stool	chromatography-quadrupole time-of-
		flight mass spectrometry
Bile acid re-absorption	Bile acid concentrations	Ultra-high-performance liquid
	in blood and feces	chromatography-quadrupole time-of-
		flight mass spectrometry
Exploratory/Other	•	

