A sample size of 12 per group provides 80% power to detect a 50% difference in proportions of participants between groups by chi2 test experiencing a laboratory abnormality or adverse event at a significance threshold of α =0.05. In addition, based on our preliminary trial data for change in TNF- α , and applying a 2-sided t-test of means, n=24 allows for n=12 per arm and provides >90% power, at a significance threshold α =0.05, to detect a mean change of -0.5 =/- 0.25 pg/ml in XN-treated participants with CD, based on an estimated mean change of 0.1 +/- 0.25 pg/ml from placebo. Will we randomize up to 32 participants to allow for attrition up to 25% [resulting in a final sample of at least n=24/arm.

Based on our preliminary trial data for change in TNF- α , and applying a 2-sided t-test of means, n=24 allows for n=12 per arm and provides >90% power, at a significance threshold α =0.05, to detect a mean change of -0.5 =/- 0.25 pg/ml in XN-treated participants with CD, based on an estimated mean change of 0.1 +/- 0.25 pg/ml from placebo. Will we randomize up to 32 participants to allow for attrition up to 25% [though we had <10% attrition in our previous trial in this population] resulting in a final sample of at least n=24/arm.

15 Recruitment

Participants will be recruited from the region via posted fliers and the NUNM clinic via posted fliers and IRB-approved mailings to current patients. Members of the study team will present information about study participation to CD support and community groups and set out flyers for attendees to pick up. In addition, we will use Craigslist and social media (i.e. Facebook and Instagram) as well as the NUNM weekly newsletter. Candidates from the community would

simply respond to a dedicated study telephone line or email, and express their interest, and are then contacted by a Study Coordinator.

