Laboratory measures (including red blood cell count, white blood cell count, hematocrit (%), hemoglobin, mean corpuscular volume, AST, ALT, creatinine-estimated glomerular filtration rate (eGFR), blood urea nitrogen (BUN), and creatinine) will be analyzed by first assessing descriptive statistics including mean, median and standard deviation. All distributions will be tested for skew and transformed (e.g., natural log transformed) as needed to reduce the influence of skew in subsequent analyses. All parameters will be evaluated by formally comparing means from baseline

Protocol

to each time point by unpaired, 2-sided t-tests, as well as for trends over time by applying linear mixed ANOVA models with time point as a repeated factor.

As an element of the evaluation for safety of the intervention, the % laboratory newly abnormal (for values within the clinically normal range at baseline) per clinical laboratory reference ranges for each lab parameter will be reported at each 2-week time point and the % compared between XN and placebo groups by Fisher's exact test.

Assessment for changes in the distribution of each lab parameter will be performed by presenting means and confidence intervals (CI) for the change in each group, as well as the mean CI for the difference between groups; significance will be tested using 2-sided, unpaired t-tests (or, if inspection of distributions indicates strong non-normality, with a non-parametric Wilcoxon signed rank test) of the mean values for XN compared to placebo.

Assessment for overall *increases* or *decreases* in parameters of interest will be tested for linear trends of the means by linear mixed ANOVA with time point as a repeated factor, which may be suggestive of evidence for cumulative toxicity if trending in a clinical deleterious direction.

Analysis of inflammatory cytokines, gut permeability biomarkers, and endotoxemia:

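### Aim 1's margin of 50% more affected participants is neither what section 14 powers nor what section 20a tests, and as a raw-count rule it separates safe from harmful products poorly

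*Protocol*

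**What the plan says.** Four places in the protocol describe the primary safety question.

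- **Section 7, Aim 1** states the primary hypothesis for those given XN as follows: "number of participants with an adverse event or abnormal lab value will not be more than 50% higher than the number in the placebo" arm. This is a relative margin on numbers of participants, for a composite of adverse events (AEs) and laboratory values.
- **Section 12, Table 1** gives the primary measure as "Liver (AST, ALT, GGT) and renal function (eGFR, BUN:Cr) tests plus hematology (CBC"). AEs are not in that row.
- **Section 14** states: "A sample size of 12 per group provides 80% power to detect a 50% difference in proportions of participants between groups by chi2 test", the endpoint being participants "experiencing a laboratory abnormality or adverse event at a significance threshold" of 0.05. It does not say whether the 50% is absolute or relative, and it gives no placebo rate.
- **Section 20a** reports "the % laboratory newly abnormal (for values within the clinically normal range at baseline") for each parameter at each two-week visit and compares the arms by Fisher's exact test. It adds t-tests and mixed models on the laboratory values. It contains no composite, no comparison of AEs and no use of the 1.5 margin.

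**The concern.** A hypothesis that harm is not more than 1.5 times placebo calls for an analysis that can say how large the excess might be. A chi-square test of no difference cannot do that: with 12 per arm, a non-significant result is the expected outcome even if the margin is reached. The other route is to compare the two counts directly with the factor 1.5, and this ignores sampling error altogether. Either way, Aim 1 could be declared met or not met with little connection to the true effect of XN. The four sections also disagree on what counts as an event, so two analysts could follow the protocol and report different primary results.

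**Working it through.** **Inputs.** The margin of 1.5 is from Aim 1. The 12 per group, the chi-square test and the "significance threshold of α =0.05" are from section 14; two-sided testing is assumed. Section 14 says "Will we randomize up to 32 participants to allow for attrition up to 25" per cent, and 32 × 0.75 = 24, in line with "n=24 allows for n=12 per arm". (The same section also gives the final sample as 24 per arm, which 32 randomised participants cannot supply.) I use 12 per arm, with 16 per arm for no attrition. The placebo rate of the composite is not given, so a range of 10% to 90% is assumed.

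**Step 1: reproduce the stated 80%.** Power = Φ{[|p2 − p1|√n − 1.96√(2p̄(1 − p̄))] / √(p1(1 − p1) + p2(1 − p2))}. For 5% v 55%, n = 12 and p̄ = 0.30: (1.732 − 1.270)/0.543 = 0.85, so power = 0.802. The figure therefore reproduces as an absolute 50-point gap with one rate near the edge of the scale. For 10% v 60% the formula gives 0.762, and for 25% v 75% it gives 0.714 (exact chi-square 0.791 and 0.766).

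**Step 2: the same test for Aim 1's relative excess.** Exact enumeration of the uncorrected chi-square test, 12 per arm:

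| Placebo v XN | Power |
|---|---|
| 10% v 15% | 0.03 |
| 30% v 45% | 0.13 |
| 50% v 75% | 0.26 |
| 60% v 90% | 0.39 |

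Even 66% v 99% gives only 0.57 by the formula in Step 1. No relative reading comes near 80%.

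**Step 3: section 20a's test.** With no placebo events, Fisher's test on a single parameter needs 5 of 12 on XN (p = 0.037); 4 of 12 gives p = 0.093. At 16 per arm, 5 v 0 gives p = 0.043.

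**Step 4: Aim 1 as a count rule.** The rule is met if X(XN) ≤ 1.5 × X(placebo), with independent binomial counts.

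*Ceiling.* 1.5 × 8 = 12, the whole XN arm at n = 12. 1.5 × 11 = 16.5, more than the whole arm at n = 16. Beyond those placebo counts the rule cannot be broken.

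*Probability that the rule is met, 12 per arm:*

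| Placebo rate | Equal rates | True ratio 1.5 | True ratio 2 | All XN participants affected |
|---|---|---|---|---|
| 10% | 0.66 | 0.53 | 0.41 | 0.00 |
| 30% | 0.76 | 0.53 | 0.29 | 0.01 |
| 50% | 0.85 | 0.53 | 0.19 | 0.19 |
| 66.7% | 0.92 | – | – | 0.63 |
| 80% | 0.97 | – | – | 0.93 |
| 90% | 0.997 | – | – | 0.996 |

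The chance of a breach with identical rates is one minus the second column: 34%, 24% and 15% at 10%, 30% and 50%. At 16 per arm the picture is the same: the rule is met with probability 0.52 to 0.53 at a true ratio of 1.5 (placebo 10% to 50%), and 0.92 at a placebo rate of 80% with every XN participant affected.

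**The case against.** The strongest reply is that safety does not rest on one ratio. Section 11b lists AEs, new laboratory abnormalities and mean changes as safety measures. Section 21 provides an independent monitoring board and a halting rule, and section 22 provides adjudication of AEs. Aim 1 states a hypothesis and does not say that safety will be declared from raw counts. A statistical analysis plan, not shown here, may add detail. This limits the consequences, but it does not reconcile a primary hypothesis, a power statement and a methods section that address three different questions within one document.

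Some stronger readings are tempting and are not supported:

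- *That the composite has no analysis at all.* Section 14 does name a chi-square test on it. The defect is that this test addresses a different question from the margin.
- *That a favourable conclusion is close to guaranteed.* This needs a placebo rate of about 80% or more. Such a rate is plausible with AEs of any grade, questionnaires every two weeks and many laboratory tests in active disease, but the documents do not state it. At 10% to 50% the rule errs the other way, often flagging a harmless product.
- *That laboratory tests alone would saturate the composite.* This depends on treating the parameters as independent. Hemoglobin, hematocrit and red cell count move together, and eGFR is derived from creatinine.
- *That a participant who starts abnormal and worsens is never counted.* The restriction to normal baselines applies only to the newly abnormal percentage. Section 20a also analyses mean changes and trends without it, and section 12 has values interpreted against baseline.

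**Conclusion.** The point stands as a mismatch plus a poor decision rule. Aim 1's relative 1.5 margin is not powered in section 14, is not tested in section 20a, and concerns a composite that Table 1 does not list. The low power for a relative excess, the roughly even chance of passing at the margin, and the 34% to 15% chance of false breach are exact binomial results at 12 per arm for the placebo rates shown. The ceiling at 8 of 12 or 11 of 16 needs no assumption about rates. How often it would be reached does: at placebo rates of 80% or more, the rule is met with probability of at least about 0.92 even if every XN participant has an event, but that is conditional because no placebo rate is given. The need for a change does not depend on it, since the rule performs badly at low and moderate rates too.

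**What to change.** - Define one per-participant composite and use it in Aim 1, Table 1, section 14 and section 20a: a treatment-emergent AE, or a laboratory abnormality that is new or worse than the participant's own baseline, from first dose to Week 8.
- Drop the 50% count rule as a basis for concluding safety. Report the proportion per arm, and the risk difference and ratio with 95% intervals.
- Present Aim 1 as estimation. State that neither a non-significant chi-square or Fisher test nor a count ratio below 1.5 establishes safety at this size. Requiring the upper limit of the risk ratio to lie below 1.5 is not a realistic substitute. With n = (1.96 + 0.84)² × 2(1 − p)/p ÷ (ln 1.5)² (equal true rates p, one-sided 0.025, 80% power), it needs about 382 per arm at 20%, 96 at 50%, 48 at 66.7% and 24 at 80%.
- Say in section 14 that the stated power refers to an absolute difference of about 50 points, give the assumed placebo rate, and correct the final sample to 12 per arm.
- Add shift tables for parameters abnormal at baseline.

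**Cost.** Rewording of four sections and some programming on data already collected; no extra visits or participants. The safety statement becomes less favourable because the intervals are wide. As a guide, 1.96√(2p(1 − p)/n) gives a half-width of 40 points at n = 12, p = 0.5, and 32 points at n = 16, p = 0.3.

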Our primary outcome measure for this secondary objective will include fecal calprotectin and circulating levels of inflammatory cytokines as biomarkers of systemic inflammation. The sample size provides >80% power, at a threshold of alpha=0.05, for the detection of a 25% difference in marker changes in response to XN between the healthy adults in the Phase 1 trial and participants in this trial. Additionally, we will measure changes in Crohn's Disease Activity Index (CDAI) score for participants at each clinical visit to first determine eligibility and, second, compare end results to baseline for any change in score. Finally, results will be compared to the previous Phase 1 trial in healthy adults.

Aim 3. Collect samples and measure XN metabolism, gut permeability and impact on the microbiota.

We will assess XN metabolism, gut permeability and impact on the microbiota. Thus, our outcome measures for this objective include microbiota profiles, XN metabolites and bile acid metabolites.

Aim 4. (Exploratory) Generate a computational, theoretical model for assessing and understanding of the interactions between XN and the gut microbiome, and how the identified interactions may mitigate CD.

We will measure biomarkers of gut inflammation and gut integrity, and composition of intestinal microbiome species through various methods including measurement of circulating plasma endotoxin, CD14, intestinal fatty acid-binding protein, lipopolysaccharide-binding protein; lipidomic profiling; and TLR2/TLR4 activation.

8 Trial design

The design will be a triple-masked, randomized, placebo-controlled trial. Upon confirmation of eligibility and documentation of informed consent, those participants still interested and eligible to participate will be randomized to either: XN (24 mg/day plus 288 mg of rice protein plus 117.9 mg of excipients) or placebo (rice protein 288 mg/day plus117.9 mg of excipients) taken by mouth once daily for 8 weeks.

Methods Participants, interventions and outcomes

9 Study Setting

The clinical study will take place at an academic medical center, the National University of Natural Medicine's Helfgott Research Institute in Portland, OR, USA.

10 Eligibility criteria

Crohn's Disease (n=32):

Inclusion criteria

- Adults 21-70 years of age
- Active Crohn's disease not in remission based on a CDAI score >150
- Willing to take isolated Xanthohumol as a dietary supplement for 8 weeks

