To characterize inflammatory status, circulating levels of several pro-inflammatory cytokines (TNF- α , IL-1 β , IL-2, IL-6, IL-8, IL-10, and IL-12p70) will be measured in plasma samples. The method uses nanoparticles coated with capture antibodies for the selected targets, and fluorescently labeled detection antibodies to create complexes with specific fluorescent wavelengths. After incubation with the sample, the resultant suspension is analyzed by flow-cytometry, allowing quantitative determination of the concentration of the target molecules. Compared with a conventional ELISA technique, this approach requires less sample material, allowing for smaller blood draws from participants. C-reactive protein will also be measured at Quest Diagnostic Laboratory via routine methods; this biomarker will be measured with the routine safety labs measured at each bi-weekly visit.

Secondary Outcome: Change(s) in patient-reported symptoms

The Crohn's Disease Activity Index (CDAI) is a questionnaire developed to assess symptom severity in CD.¹⁷ It is primarily a research tool and has been validated for that purpose. The index consists of eight factors, summed after adjustment with a weighting factor (described in detail in section 18a). Consensus values have been established for clinically meaningful response to an intervention, and for symptom remission.

Tertiary Outcome: XN and XN metabolites

Identification and quantification of XN and the XN metabolites isoxanthohumol; 8prenylnaringenin; O-desmethylxanthohumol; dihydro-desmethylxanthohumol; α , β dihydroxanthohumol will be achieved through ultra-high-performance liquid chromatographyquadrupole time-of-flight mass spectrometry (UPLC-QTOF). This method separates chemical species using liquid chromatography, followed by identification of the resulting isolated fractions on the basis of mass-to-charge ratio.

Tertiary Outcome: Bile acids

Identification and quantification of bile acids will be achieved through liquid chromatographymass spectroscopy. This method separates chemical species using liquid chromatography, followed by identification of the resulting isolated fractions on the basis of mass-to-charge ratio.

Exploratory Outcome: Gut integrity and enterocyte damage

The intestinal barrier function will be assessed by measuring plasma concentrations of soluble CD14, intestinal fatty acid-binding protein, and lipopolysaccharide-binding protein with commercial ELISA kits.

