Given the small sample size of these clinical trials, results related to changes in inflammatory cytokines (IL-1 β , IL-2, IL-6, IL-8, IL-10, TNF- α , and IL-12p70), gut permeability biomarkers (CD14, intestinal fatty acid binding protein) and markers of endotoxemia (LPS, LPS-binding protein) are considered preliminary, and thus our principle assessment will be measurement of effect size as *Cohen's d* statistic between XN- and placebo-treated groups at each 2-week interval compared to baseline, with the primary comparison being between baseline and week 8. We will also perform formal statistical comparisons as unpaired, 2-sided t-tests (or, if inspection of distributions indicates strong non-normality, with a non-parametric Wilcoxon signed rank test) of the means at relevant time points. The following findings will be considered evidence of possible effects: 1. Clinically and statistically significant effects for changes in cytokines of interest and/or 2. Calculation of a Cohen's d value for effect size estimation greater than 0.5 (with larger d indicating a larger potential effect size).

Assessment for overall *increases* or *decreases* in parameters of interest will be tested for linear trends of the means by linear mixed ANOVA with time point as a repeated factor. Trends will be considered significant if p<0.05 for the model overall.

Analysis of XN, its metabolites, and BAs to determine a small molecule signature of longer-term oral treatment with XN:

We will identify and quantify XN and XN-derived metabolites in plasma, stool, and urine samples. Bile acid profiles will also be determined in the stool samples. The metabolite profile data will then be used for correlation with the time-resolved gut microbiome analysis. This approach will allow us to determine links between metabolite profiles and gut microbiome compositions.

Protocol

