We will apply systems biology tools to quantify how an individual's inflammation state, as measured by calprotectin, changes over time in association with XN metabolite status and microbial taxa, their genes, gut metabolites, or BAs. To link the time dependence of inflammation to these various parameters, we will follow our prior work and construct compound Poisson generalized linear models (CPGLMs) that allow us to test for differences in temporal trends in the relative abundance of specific OTUs, genes, metabolites, or BAs as a function of various experimental parameters.²⁸ CPGLMs include a point mass at zero as well as a weighted mixture of Poisson and gamma distributions. These features enable accurate modeling of the sparse (zeroinflated) but otherwise continuous and non-normal data usually produced during microbiome and metabolome investigations.²⁸ CPGLMs also correctly account for multiple sources of variation due to different experimental parameters (e.g., XN metabolite status, inflammation state, time, and sex).²⁹ We will construct CPGLMs that model how the temporal variation of each OTU, gene, or metabolite (i.e., response variables) relates to these experimental parameters. We will adopt a stepwise approach to model construction and optimal models will be identified. Models will include interaction terms that consider co-dependencies among the experimental parameters. Random intercepts and time slopes for each individual will be included in the model to account for within-individual correlation of a response variable's abundance over time. Response variables that manifest as significantly different slopes as a function of XN metabolite status are those variables that putatively interact with XN metabolites. Related analyses of model slopes will resolve parameters that elicit dependencies with inflammation state, as well as parameters that vary

Protocol

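### Fecal calprotectin, named first in Aim 2's primary outcome measure, has no stated XN-versus-placebo comparison, and no Aim 2 marker is named as the lead contrast

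*Protocol*

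**What the plan says.** **Objective.** Protocol section 7, Aim 2: "Our primary outcome measure for this secondary objective will include fecal calprotectin and circulating levels of inflammatory cytokines". Section 12 lists the cytokines: "circulating levels of several pro-inflammatory cytokines (TNF- α , IL-1 β , IL-2, IL-6, IL-8, IL-10, and IL-12p70". That is seven, so Aim 2 has eight markers, with no ranking among them. Table 1 lists calprotectin and CRP as secondary outcomes.

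**Power.** Section 14 has two bases. The first is a safety comparison of proportions. The second is "based on our preliminary trial data for change in TNF"-alpha: "applying a 2-sided t-test of means, n=24 allows for n=12 per arm and provides >90% power", "to detect a mean change of -0.5 =/- 0.25 pg/ml in XN-treated participants with CD", against a placebo change of 0.1 with the same SD. The power sentence inside Aim 2 is different. It is "for the detection of a 25% difference in marker changes in response to XN between the healthy adults in the Phase 1 trial" and participants here; it names no marker and does not compare XN with placebo.

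**Between-arm analysis.** Section 20a, on cytokines, gut permeability and endotoxemia, specifies Cohen's d and unpaired two-sided t-tests between XN and placebo, with baseline to Week 8 as the main comparison. It names the seven cytokines, CD14, intestinal fatty acid-binding protein, LPS and LPS-binding protein. One of its two criteria for a possible effect is "Clinically and statistically significant effects for changes in cytokines of interest"; the other, joined by and/or, is d above 0.5.

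**Calprotectin.** Section 20a mentions it only under longitudinal regression modeling, which asks how "inflammation state, as measured by calprotectin, changes over time in association with XN metabolite status" and microbial or metabolite features.

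**The concern.** The objective, the power statement and the analysis point to three different places. The marker named first for Aim 2 has no stated comparison by randomised arm. The marker with a power statement is not designated as the lead. The significance criterion names no marker.

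XN metabolite status is measured after randomisation and reflects adherence, absorption and each participant's microbiome as well as assignment. An association between it and calprotectin is useful for mechanism, but randomisation does not protect it from confounding. If section 20a is followed as written, a Crohn's disease trial could report on gut inflammation with no XN-versus-placebo estimate. With no lead marker among the cytokines, emphasis can also settle after the fact on whichever one looks best.

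**Working it through.** **1. Setting the sections side by side**

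| Marker | Aim 2 primary measure | Table 1 level | 20a between-arm list | 20b ANCOVA list | XN-vs-placebo power (14) |
|---|---|---|---|---|---|
| Fecal calprotectin | yes, named first | secondary | no | no | no |
| TNF-alpha | yes | secondary | yes | yes | yes |
| Six other cytokines | yes | secondary | yes | yes | no |
| CRP | not named | secondary | no | no | no |
| Permeability and endotoxemia markers | no | exploratory | yes | yes | no |

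Exploratory markers receive the randomised contrast while two secondary outcomes do not. Section 20b presents its list as what is meant by all tests of mean differences, so it repeats the omission.

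**2. The plan's own power figure**

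Inputs from section 14: changes of -0.5 and 0.1 pg/ml, SD 0.25, 12 per arm, two-sided 0.05.

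- Difference = 0.1 - (-0.5) = 0.6; standardised, 0.6 / 0.25 = 2.4.
- Noncentrality = 2.4 × √(12/2) = 5.88, with 22 degrees of freedom and critical t of 2.074.
- Power = 99.99%, which agrees with the stated figure of more than 90%.
- Attrition: 32 × (1 - 0.25) = 24, or 12 per arm.

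**3. Chance findings among the seven cytokines that 20a tests**

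If independent, with no true effect:

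- either direction: 1 - 0.95^7 = 0.302;
- one given direction, same two-sided tests: 1 - 0.975^7 = 0.162.

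The protocol gives no correlations, so a range is assumed. Simulated null trials with seven equally correlated normal markers, 12 per arm and a two-sided 5% t-test at Week 8 give:

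| Assumed correlation | At least one p<0.05, either direction | Favourable direction only |
|---|---|---|
| 0 | 30% | 16% |
| 0.5 | 23 to 24% | 12% |
| 0.8 | 15% | 7 to 8% |

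With 16 per arm the results are the same to within about one percentage point. All these rates precede the requirement that the effect also be clinically significant.

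**4. What a calprotectin comparison could detect**

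With 12 per arm, two-sided 0.05, a t-test detects 1.20 SD with 80% power and 1.39 SD with 90%. No calprotectin SD is given, so this cannot be put into assay units or compared with an expected effect.

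**5. Cost of a formal adjustment over all eight markers**

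At 0.05 / 8 = 0.00625, TNF-alpha power is 99.6%, but that rests on an assumed 2.4 SD effect. For any marker the difference detectable with 80% power at 12 per arm rises from 1.20 to 1.60 SD.

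**The case against.** Aim 2 is a secondary objective; the primary hypothesis is safety. Section 20a calls the cytokine results preliminary because the trial is small, makes effect size the main assessment, and already fixes Week 8. Its significance criterion requires clinical as well as statistical significance and yields only evidence of a possible effect. All of this stands. A reader might infer that Aim 2 can be claimed on any marker with p<0.05; the text does not say that.

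A reader might also infer that the trial was sized on TNF-alpha alone. It was not: section 14 first gives the safety proportions.

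The analysis plan is not shown and may compare calprotectin by arm. Nothing in the protocol forbids it, so it would be too strong to say that calprotectin will never be compared. For CRP, the schedule draws it with the safety labs, and the laboratory list in 20a is worded as open-ended, so CRP could be read into that analysis, although it is not named. The point about calprotectin survives because it does not rest on silence. The protocol writes out a between-arm list, leaves out the first marker it named for the aim, and gives that marker a different, non-randomised analysis.

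Finally, familywise control across preliminary secondary markers is a matter of judgement. Adjusting the t-tests would also leave the d>0.5 route open. At 12 per arm that route is met by chance in either direction in 23.4% of null trials for each marker. This objection also stands.

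**Conclusion.** The point holds as an inconsistency within the protocol. Calprotectin is named first in Aim 2's primary outcome measure but is absent from the between-arm analysis and from the ANCOVA list; CRP is not named in either. TNF-alpha, the one Aim 2 marker with an XN-versus-placebo power statement, is not designated as the lead.

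The chance of at least one significant cytokine under no effect is about 15 to 30% in either direction and 7 to 16% in the favourable direction. These figures assume seven equally correlated, normally distributed markers with correlation 0 to 0.8, tested once at Week 8, and precede the clinical-significance condition. They describe the room for selective emphasis and are not the error rate of a formal Aim 2 claim. Counting eight tests would overstate the present plan, since calprotectin is not among those listed.

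The documents do not support reading this as a failure of formal error control that requires a multiplicity procedure. The correction is worth making because it is specific and cheap.

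**What to change.** - In section 20a, add fecal calprotectin and CRP to the XN-versus-placebo analysis of change from baseline to Week 8, and add both to the ANCOVA list in 20b.
- In Aim 2 and 20a, name the TNF-alpha change to Week 8, XN minus placebo, as the lead Aim 2 contrast, because section 14 provides its power. Place calprotectin next and label the other markers supportive. If the sponsor prefers calprotectin as the lead on scientific grounds, section 14 would need an SD and a target difference for it.
- Keep the regression on XN metabolite status, labelled as mechanistic.
- Holm across the eight markers is optional and not required for preliminary secondary outcomes.

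The cost is wording plus two further between-arm comparisons on samples already scheduled; no participants, visits or assays are added. The limitation is that calprotectin power cannot be stated in its own units until an SD is supplied.
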